-Testing hypothesized differences between experimental and control groups will use an intent-to-treat analysis that includes all participants randomized. LGM will examine the effect of treatment condition on trajectories of change separately for each of the outcomes over the one-year follow-up. To test Hypothesis 1, we will assess the trajectories of the mothers' outcomes (mental health, physical health, substance abuse, etc.) and predict of the trajectory of change by intervention condition (Healthy Home vs. TAU). Controlling for the effects of socio-demographic variables and pretest levels of the dependent variables is possible in LGM, if these variables are found to differ by randomization group. To test Hypothesis 2, a similar procedure will consider children's outcomes (mental health, physical health, behavior problems, etc.).

- Testing mechanisms of action. Using Mplus 6, this set of analyses will investigate links between trajectories of change (growth curves) for the hypothesized mechanism of action variables (mediators) and trajectories of mothers' outcomes or children's outcomes following MacKinnon, Lockwood, Hoffman, West and Sheets' (2002) procedures. This method is more powerful than the classic (Baron & Kenny, 1986) method, particularly for binary outcomes. LGM can also test multiple indirect paths or mediators (i.e., Hypothesis 3c) with this method.

- Clinically significant change procedures (Jacobson & Traux, 1991) can also investigate efficacy of an intervention. These procedures: 1) determining whether participants have made statistically reliable change and 2) categorizing subjects according to clinically meaningful cut-points, e.g., recovered (statistically reliable change that moves a client out of clinical range), improved (statistically reliable improvement, but still in the clinical range), and unimproved/deteriorated.

-Implementation analysis will be used to determine the feasibility of adapting Healthy Home for other agencies. Using cost logs for training and service delivery, the total cost of

implementing Healthy Home can be determined. Therapist and agency satisfaction as well as therapist fidelity to Healthy Home will be assessed to determine if changes to the Healthy Home implementation protocol are needed.

-Mothers will have additional data from baseline assessments administered by the treatment agency: a GAIN-I administered at treatment intake and a GAIN-M90 administered 90 days into treatment. As noted in the measures section, several variables (e.g., demographics, history of abuse) will be taken from the GAIN-I. There are a number of follow-up analyses that may provide greater understanding of the direct and interactive relationships between symptoms, intervention, and post-treatment substance use, including adding to growth models of mental or physical health and examining moderators of treatment effects. [The GAIN is no longer being used in the study]

- Proposed moderators will be used in two types of analyses. The variables might predict trajectories of change of the mothers' and children's outcomes, only. For example, does poor sleep contribute to early relapse for mothers in recovery? The moderators might also interact with treatment. For example, do mothers from different ethnic groups respond differently to Healthy Home? Effect sizes will be generated for future intervention development/refinement from the results of these exploratory analyses.

- Secondary data analysis will be used to examine data extracted from clinical intervention forms related to health assessments, recommendations/referrals, treatment/services rendered, follow-up plan of care, and education provided to individuals during home health visits.

- Missing data and attrition patterns will be examined. In research with samples of individuals in substance use recovery some loss to follow-up is expected. Our proposed methods allow the inclusion of cases with randomly missing data, we will test for non-randomness, i.e., a non-ignorable or informative missing data pattern (Little & Rubin, 1987). If there is differential attrition by condition, alternative models will be examined (in addition to the proposed) which account for or model the attrition mechanism (Angrist, 1997; Heckman, 1979; Idson & Feaster, 1990) to produce a more robust range of estimates.

Privacy/Confidentiality Agreements

4.13. **Describe any privacy agreements or certificates of confidentiality, if applicable.**
We have received a certificate of confidentiality from NIH.

4d. Description of Study (cont'd)

Deception

4.14. *** Is the use of deception part of the study design?**

Yes No

If yes, please answer the following 3 questions:

4.14.A. **Describe in detail the nature of the deception and explain why this is necessary for the research.**

4.14.B. **State how, when, and by whom the research subjects will be debriefed.**

4.14.C. **Upload a copy of the debriefing script.**

5. Study Participants

Per 45 CFR 46, human subjects (participants) means a living individual about whom an investigator (whether professional or student) conducting research obtains:

1. data through intervention or interaction with the individual; or
2. identifiable private information (i.e. pathological specimens, medical records, etc.)

5.1. * Participant Age:

Check all that apply	Notes
 0-6	Parent Permission/Consent required for each participant
 7-17	Parent Permission/Consent & Child Assent required for each participant
 18-65	Consent required for each participant unless a waiver of consent is approved by the IRB
 65+	Consent required for each participant unless a waiver of consent is approved by the IRB

5.2. For the following questions, please use integers for your responses. For any question that is not applicable, please enter the number 0. (Do not enter commas, decimal points or special characters)

5.2.A. * Maximum number of subjects in the Protocol to be *screened* at all sites (regardless of PI):
1000

5.2.B. * Total number of subjects in the Protocol to be *studied* at all sites (regardless of PI):
800

University of Miami

5.2.C. * Maximum number of subjects to be *screened* by this PI at UM:

0

* Maximum number of subjects to be *enrolled* by this PI at UM:

0

* From the above, how many are expected to *complete* this study (participate in the study beyond initial enrollment)?

0

Jackson Health Systems

5.2.D. * Maximum number of subjects to be *screened* by this PI at ***Jackson Health Systems (JHS)***:

0

* Maximum number of subjects to be *enrolled* by this PI at ***Jackson Health Systems (JHS)***:

0

* From the above, how many are expected to *complete* this study (participate in the study beyond initial enrollment)?

0

Miami VA Medical Center

5.2.E. * Maximum number of subjects to be *screened* by this PI at *Miami VA Medical Center*:

0

* Maximum number of subjects to be *enrolled* by this PI at *Miami VA Medical Center*:

0

* From the above, how many are expected to *complete* this study (participate in the study beyond initial enrollment)?

0

5a. Study Populations

5.3. * Study populations to be included in this study where PI will be conducting research and those sites where the UM IRB will have oversight responsibility:

Check all that apply Notes

Normal, healthy volunteers

Children/minors
(under 18 years of age)

Poor/uninsured

Pregnant women/fetuses Specific Florida statutes apply to prohibit the use of any live fetus or live, premature infant for any type of scientific, research, laboratory or other kind of experimentation except as necessary to protect or preserve the life and health of such fetus or premature infant.

Outpatients

Wards of the state Specific Florida statutes apply to prohibit the enrollment of a minor/adult, for whom a guardian has been appointed by the court, in a research study without first acquiring the approval of the court having jurisdiction of the ward.

5.3.A. If *other*, please specify:

5.3.B. **Describe below any additional safeguards that have been included to protect vulnerable subjects:**

Study candidates will be told that their participation is voluntary, that they may withdraw consent at any time, and that their decisions regarding participation will not affect their relationship with Banyan or UM.

This study population includes children. With IRB approval and following legally-established procedures, we plan to enroll children who are wards of the state.

We do not anticipate enrolling prisoners, and subjects who become incarcerated after the study begins will not be involved in human subjects activities during their

incarceration. Participants are also told that if they are on probation or parole there will be no special privileges given by the courts because of their participation in the study.

Pregnant women may be enrolled in the study. Interventions are behavioral with some minimal physical procedures for assessment, and data collection involves minor physical procedures the most invasive of which are collection of urine samples, which pose no foreseeable risks to pregnant women, fetuses or neonates. It is possible that some pregnant minors (children of the index women) may be enrolled. Children do not have any physical procedures in the assessment portion of the study and physical procedures in the intervention portion are limited to minimally invasive physical procedures. Children age 7 or above will be assented.

We have received a certificate of confidentiality.

5b. Inclusions/Exclusions

5.4. * Is the population being enrolled in this study at high risk for incarceration?

Yes No

5.4.A. If yes, will the subjects be withdrawn from the study once they are incarcerated?

Yes No

5.4.A.(i) If the above answer (question 5.4.A.) is no, describe how re-contacting/re-consenting, treatment, and/or follow-up will occur:

We will not conduct study procedures with participants while they are incarcerated but will not withdraw them from the study as they may be available to conduct study procedures upon release if they are still within the study timepoint windows. If a mother is incarcerated we will attempt to conduct follow-up assessments within the appropriate timepoint windows with children enrolled in the study if they can be accompanied by an adult family member.

NOTE: If a subject becomes incarcerated while enrolled in a study, all research interactions and interventions with that subject, and the obtaining of identifiable private information about the subject, must cease until the requirements of subpart C have been satisfied with respect to the relevant protocol.

If notified that a previously enrolled research subject has become a prisoner, the principal investigator must promptly seek IRB re-review of the protocol in accordance with the requirements of subpart C if the principal investigator wishes to have the prisoner-subject continue to participate in the research. In special circumstances in which the principal investigator asserts that it is in the best interests of the subject to remain in the research study while incarcerated, the IRB Chairperson may determine that the subject may continue to participate in the research until the requirements of subpart C are satisfied.

5.5. * What are the criteria for exclusion of participants from the research?

Persons who do not meet the inclusion criteria listed below will be excluded.

5.6. * Will any population be systematically excluded in this study?

Yes No

5.6.A. If yes, provide rationale/justification for this exclusion:

5.7. * What are the criteria for inclusion of participants in the research?

To be eligible for the study Mothers must meet all of the following criteria: (1) Enrolled in outpatient substance abuse or mental health treatment (or treatment for substance abuse as a co-occurring disorder) or case management for mental health or substance abuse problems, (2) have at least one child age 0-17 with whom she has at least monthly contact (3) be age 18 or above, (4) capable of giving informed consent and comprehending either English or Spanish, (5) willing and able to participate fully in the protocol (e.g., to accept assignment to either condition, to provide sufficient locator information for follow-up, to allow their treatment sessions to be monitored for fidelity/process assessment and supervision).

To be eligible for the study Children must meet all of the following criteria: (1) biological, step or adopted child of a mother enrolled in the study and with whom the mother has at least monthly contact (2) age 2-17, (3) has the signed permission of a legal guardian to enroll in the study, (4) gives assent to participate in the study if age 7 or above.

5.8. * Will only one group of individuals be systematically selected and recruited for this study (e.g., welfare patients, racial and/or ethnic minorities, persons confined to institutions or persons determined to be incapacitated)?

Yes No

5.8.A. If yes, please state how this participant group will benefit from the results of the research and provide the reasons and justifications to target this group:

This study focuses on women in substance abuse/mental health treatment and their children. These groups are at high risk for significant health consequences and there is a need for culturally-informed interventions tailored to address their unique needs.

5c. Research Involving Pregnant Women or Fetuses

Pregnant woman or fetuses may be involved in research if **ALL** of the following conditions are met (all items must be justified):

(a) **Where scientifically appropriate, preclinical studies, including studies on pregnant animals, and clinical studies, including studies on nonpregnant women, have been conducted and provide data for assessing potential risks to pregnant women and fetuses.**

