University of Miami - Miller School of Medicine

Set-Enhanced Aftercare for Mothers in Substance Abuse Recovery and Their Children

Version Date 6-7-2016

National Clinical Trial Number: NCT02702193

[name]

4. Description of Study

Study Protocol

4.1. * Abstract and Specific Aims

Include a brief summary of the significance, purpose or research question, specific aims, and risks/benefits. Specific aims include hypotheses you will investigate.

The study will conduct a translational randomized trial comparing an adaptation of Structural Ecosystems Therapy (SET), "Healthy Home", as an enhancement of substance abuse or mental health outpatient treatment, to outpatient treatment as usual (TAU) among approximately 172 Black, Hispanic and White non-Hispanic mothers enrolled in outpatient substance abuse, mental health or substance abuse as a co-occurring condition treatment. The study will be conducted with a community partner, Banyan Health Systems (also known as Miami Behavioral Health and Spectrum Programs), that delivers integrated substance abuse/mental health treatment and primary care. Agency staff will conduct data collection and agency nurses will deliver Healthy Home. Data will be collected at baseline and 4, 8, and 12 months post-randomization.

The Specific Aims of the proposed study are to:

- 1) test the effectiveness of SET for improving physical and mental health and reducing relapse of mothers in substance abuse/mental health recovery;
- 2) test the effectiveness of SET for improving health and mental health outcomes of children of mothers in recovery;
- 3) test mechanisms of action of SET (self care, environmental risk, family functioning and stigma);
- 4) assess SET implementation and sustainability factors and the relationship between fidelity and outcomes; and
- 5) examine the interactions of ethnicity and ethnicity-related factors on outcomes.

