Mother's in recovery qualitative study. Thirteen mothers currently or recently discharged from substance abuse treatment at Banyan were interviewed regarding family influence on treatment, recovery and relapse, and attitudes/preferences regarding family aftercare. Preliminary review (formal content analysis is ongoing) suggests the following themes: 1) Children and family are the major motivation to remain substance-free; 2) Partner relationships, stress, family problems, shame/guilt, depression and environmental cues are the most challenging for abstinence; 3) Mothers want to involve supportive family members (especially children) in a home-based family aftercare intervention to address family healing, improve communication and support, establish family boundaries, re-establish maternal roles and repair parent-child relationships.

- 4.3. **If you have cited references above, please attach a bibliography, including title, full author list, journal, date and pages. This bibliography should include only those articles referenced above.**

Name	Description	Version
SET R Refs for IRB.docx		0.01

4a. Description of Study (cont'd)

Rationale and Methodology

- 4.4. *** In non-technical, lay language, describe the study design and all study procedures, in order of sequence and timing. Include length of subject participation, what tasks are involved in the study, what tests or procedures subjects will be asked to complete or undergo, specific measures to be used, etc. If applicable, include frequency of visits, duration of visits, and study procedure calendar.**

Study design: The study uses a mixed design in which mothers who are enrolled in outpatient substance abuse/mental health treatment (or treatment for substance abuse as a co-occurring condition) will be randomized to outpatient substance abuse/mental health (or co-occurring) treatment enhanced by Healthy Home (TAU + Healthy Home) or outpatient substance abuse/mental health (or co-occurring) treatment as usual (TAU). Mothers and their minor children enrolled in the study (ages 2-17) will be assessed 4 times at 4 month intervals: Baseline, 4 months, 8 months, and 12 months (with a window for final assessment up to 18 months). Randomization will take place after the baseline assessment.

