QA monitoring will be conducted by staff of El Centro according to the standard procedures which include a QA review prior to initiation, upon conducting baseline procedures with the

first few study participants, and then for interim reviews.

4.12. * Support the study validity by describing the statistical design, including quantitative and qualitative methods used to analyze data.

The following is the planned data analysis procedure as submitted in the grant application.

-Testing of data quality and distributional assumptions.

Distributions and frequencies of all measures will be examined for non-normality and transformed as needed. If transformation is not sufficient, other distributions (Poisson, Negative Binomial) or nonparametric analyses will be used. Internal consistency will be reported for all measures with Cronbach's alpha. If any scale alphas are below .70, item total correlations and/or factor analysis will be employed to diagnose the psychometric problems and new scales with higher internal consistency will be considered.

-Evaluating the effectiveness of randomization will be accomplished by use of ANOVA and Chi-square of baseline variables. Although not anticipated, if variables with theoretical importance to outcomes show baseline differences by condition, hypotheses tests will statistically control for (baseline) differences.

-Growth curve analysis. Latent growth modeling (LGM) in Mplus 6 (Muthén & Muthén, 2010) will examine change over time in the outcomes. LGM involves creating latent variables representing growth parameters (the baseline or intercept; the linear slope or rate of change, the quadratic slope, etc.). It allows for the simultaneous estimation of multiple growth functions with growth parameters of one function related to growth parameters of another. Mplus allows for outcome variables with distributions that are not continuous (e.g., Poisson for skewed variables or logistic for binary outcomes), which is particularly important with substance use and health outcomes. LGM can generate effect sizes for rate of change or the difference at a single time between the two conditions, i.e., Cohen's d (Cohen, 1992). Following Cohen's (1992) guidelines, we will interpret our effect sizes using the convention of "small" ($d = .2$), "medium" ($d = .5$), and "large" ($d = .8$).

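### Does accepting the 12-month assessment up to month 18 undermine an analysis of one year of follow-up?

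*Combined protocol and SAP*

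**What the plan says.** Section 4.1 gives the schedule without a window: "Data will be collected at baseline and 4, 8, and 12 months post-randomization". Section 4.4 (Study design) repeats the four assessments and adds the window on the last: "12 months (with a window for final assessment up to 18 months"). Section 5.4.A.(i) also treats visits as belonging to windows. An incarcerated mother may resume study procedures "upon release if they are still within the study timepoint windows", and staff will meanwhile try to "conduct follow-up assessments within the appropriate timepoint windows with children enrolled in the study".

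The analysis text in section 4.12 opens with "The following is the planned data analysis procedure as submitted in the grant application". It plans latent growth models whose parameters include "the linear slope or rate of change, the quadratic slope, etc", says these can yield "effect sizes for rate of change or the difference at a single time between the two conditions", and tests condition on "trajectories of change separately for each of the outcomes over the one-year follow-up". It never mentions the window. It gives no time scores, no rule for a final visit after month 12, no rule for choosing the curve shape, and no named time for the arm difference.

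**The concern.** A final visit at month 18 is 6 months late, or 1.5 times the 4-month interval between visits. Section 4.12 permits three treatments of it: leave it out as beyond one year, score it as month 12, or enter it at its actual month. These are different tests of Hypotheses 1 and 2.

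Scoring a late visit as month 12 steepens a slope that is still rising. Using actual time on a straight line flattens a slope that has levelled off. If lateness differed by arm, either could create an arm difference where none exists. If the coding were picked after seeing results, the error rate would rise even with equal lateness. The open curve shape and contrast add further choices. Under the incarceration provision, a mother's and a child's final visits could also fall months apart, which might blur mediator models linking the two.

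**Working it through.** **Inputs.** From the documents: visits at 0, 4, 8 and 12 months, the last accepted to month 18 (sections 4.1 and 4.4), and about 172 mothers (section 4.1). The plan states no alpha, power, SD, allocation ratio or lateness rate, so it has no figure of its own to reproduce. Assumed: 86 mothers per arm (1:1), outcome SD 1, correlation 0.5 between visits, two-sided 5% tests, and late visits spread evenly over 0 to 6 months past month 12 (mean 3 months).

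**Late visits scored as month 12, change continuing.** The mean time is 6, the deviations are −6, −2, 2, 6, and their squares sum to 80. The last visit therefore has slope weight 6/80 = 0.075. With mean delay L, the slope is multiplied by 1 + 0.075L.

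| Share late | L (months) | Slope too large by |
|---|---|---|
| 10% | 0.3 | 2.3% |
| 30% | 0.9 | 6.8% |
| 50% | 1.5 | 11.3% |

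Equal delay multiplies both arms alike, so with no true effect the false difference is zero.

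**Unequal delay.** With shared yearly change C and a difference D between the arms in mean delay, the false 12-month difference is 0.075 × D × C. For 20% against 50% late, D = 1.5 − 0.6 = 0.9.
- The standard error is 12 × √(2 × 0.5 / (86 × 80)) = 0.145.
- C = 0.5 SD: bias 0.034, or 0.23 standard errors, giving about 5.6% false positives (simulation 5.9%).
- C = 1.0 SD: bias 0.068, or 0.47 standard errors, giving about 7.5% (simulation 7.4%).

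**Simulated false-positive rates** (4,000 runs per case, Monte Carlo error about 0.35 points). Left out means that final visits more than 1 month late are set missing; that limit is assumed.
- 30% late in each arm, C = 1.0 SD: all three codings 4.6% to 6.0%.
- 20% against 50% late:

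| Shared change | As month 12, C = 0.5 / 1.0 | Actual month, C = 0.5 / 1.0 | Left out, C = 0.5 / 1.0 |
|---|---|---|---|
| Continues | 5.9 / 7.4% | 5.2 / 5.1% | 4.7 / 4.8% |
| Level from month 12 | 5.9 / 5.0% | 6.0 / 9.4% | 5.0 / 5.0% |
| Level from month 4 | 5.8 / 5.5% | 6.2 / 10.8% | 5.5 / 8.4% |
| Reverses at month 12 | 5.4 / 8.2% | 8.0 / 20.9% | 5.1 / 5.3% |

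**Effect on a true difference** of 0.40 SD, 30% late in each arm. The mean estimate is shown first if the effect keeps growing, then if it levels off at month 12: scored as month 12, 0.424 / 0.398; actual month, 0.398 / 0.363; left out, 0.398 / 0.398. The largest error is 0.037 SD, about a quarter of the standard error (0.037/0.145 = 0.26).

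**Choosing the coding afterwards.** Equal lateness, no trend, no effect, smallest p of the three codings: 6.9%, 7.8% and 8.7% at 10%, 30% and 50% late. A repeat run gave 6.6%, 7.5% and 8.4%. In that run, the two codings that keep late visits gave 5.4%, 5.9% and 6.1%. Most of the excess therefore comes from leaving late visits out.

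**Curve shape.** For an arm difference d reached at month 4, the linear slope over 12 months is:
- held to month 12: 12 × (−0.025 + 0.025 + 0.075)d = 0.90d;
- fading steadily to zero by month 12: 12 × (−0.025 + 0.0125)d = −0.15d.

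These figures have every visit on time, so they do not depend on the window.

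**The case for a change.** The strongest opposing case is that the plan fixes neither time coding, shape nor contrast, and that no straight-line coding is safe for every trend if lateness differs by arm. That is correct, and the 20.9% above shows it. But that cell needs 20% against 50% late together with a shared change of 1.0 SD per year that turns exactly at month 12. The documents show none of these conditions, and section 4.4 gives the same monthly contact calls to all enrolled women.

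The shape and contrast point is heavier. The intervention lasts 4 months, so a fading effect is plausible. Picking between the linear slope and the month-12 difference after seeing the data gives about 9% error per outcome; picking among four contrasts gives about 13% to 14%. This stands as a caution about after-the-fact choice. It would be the same with no window, and the plan does not prescribe such a choice.

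A piecewise model (months 0–4 and 4–12, plus a term for months past month 12) held 4.6% to 5.7% at 20% against 50% late. Its cost looks small: standard error 0.148 against 0.145, and power 78% to 82% against 79% to 83%. However, most of the test curves bend at months 4 or 12, where the model is built to bend. A straight line in actual time had a standard error of 0.133 and is free of timing bias when the trend is linear. The piecewise covariate has no value for a mother without a final visit. Nor was the model tried on the binary and count outcomes that section 4.12 allows. Statisticians could reasonably prefer individual visit times.

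On mother and child visits falling apart, the documents give no frequency of incarceration, and no effect has been computed.

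**Conclusion.** No change to the plan follows. A visit labelled 12 months with a stated window, in a document that elsewhere speaks of visit windows, does not contradict a one-year analysis. Leaving late visits out is the strained reading. A window to month 18 exists so that those visits can be used, and section 4.12 analyses everyone randomised and keeps incomplete cases. What remains is whether to use nominal or actual time. Analysts fitting a growth model settle that routinely, and no rule in the plan forces a wrong answer.

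The size is small under similar lateness: 4.6% to 6.0% false positives for any single coding, and at most about a quarter of a standard error in a true 0.40 SD effect with 30% late in each arm. With 20% against 50% late and a 0.5 SD shared change, the range is 4.7% to 8.0%. These figures assume 86 per arm, correlation 0.5, continuous outcomes and evenly spread delays; the documents supply no lateness data. The conclusion would weaken if lateness differed sharply by arm alongside a strong shared trend, or if coding, shape or contrast were chosen with the arm results in view. If lateness depended on the outcome itself, no time coding would correct it; section 4.12 already plans alternative models where attrition differs by condition.
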